6.4. Exploratory Efficacy Variables and Analysis

The exploratory efficacy endpoints are listed in Section 2.2.3.

6.4.1. Variable Definition

6.4.1.1. Electronic Headache Diary Data

The percent reduction in the monthly average number of headache days of at least moderate severity during the 12-week period after the 1st dose of study drug will be calculated by formula (4) in Section 6.1. The patient is considered as a responder reaching 50%, 75% or 100% reduction if his/her percent reduction is 50% or more, 75% or more, or 100% respectively. Similar definition will be applied to calculate the proportion of patients reaching at least 50%, 75% or 100% reduction in the monthly average number of migraine days during the 12-week period after the 1st dose of study drug. If a patient is early discontinued from the study, he/she will be counted as a non-responder.

The percent reduction in the monthly number of headache days of at least moderate severity during the 4-week period after each dose for months 1, 2, and 3 will be calculated by formula (4) where the postbaseline value will be the number of headache days of at least moderate severity prorated to 28 days for month 1, month 2, and month 3, respectively. If the patient has 50% reduction or more in month 1, he/she will be considered responder during the 4-week period after 1st dose of study drug. In addition if the patient also has 50% reduction or more in month 2 and 3, he/she is a responder for months 2 and 3, and the level of effect is sustained throughout the 12-week period after the 1st dose of study drug for this patient. Similar definition will be applied to calculate the proportion of patients reaching at least 75% reduction in the number of headache days of at least moderate severity during the 4-week period after the 1st dose of study drug for whom this level of effect is sustained throughout the 12-week period after the 1st dose of study drug. The proportion of patients reaching at least 50%, and 75% reduction in the number of migraine days during the 4-week period after the 1st dose of study drug for whom this level of effect is sustained throughout the 12-week period after the 1st dose of study drug will be derived similarly.

The headache day of any severity will be defined as a calendar day (00:00 to 23:59) with headache pain that lasts ≥ 4 hours of any severity or a day when the patient used acute migraine-specific medication (triptans or ergots) to treat a headache of any severity or duration.

The change from baseline in the monthly average number of days or hours of exploratory efficacy variables (e.g., days of headache with at least moderate severity, days of headache with any severity, total hours of headache with at least moderate severity, total hours of headache with any severity, days of use of migraine-specific acute medications, days with nausea or vomiting, days with photophobia and phonophobia etc.) **during the 12-week period** after the 1st dose of study drug will be derived similar to the primary variables using the e-diary data collected through the corresponding headache diary questions ([Appendix A](#)). The baseline values and the postbaseline values will be derived using formula (3) and (1) in Section 6.2.1 respectively, and **the change** is calculated as **postbaseline value – baseline value**.

The change from baseline in the monthly number of days or hours of exploratory efficacy variables (e.g., days of headache with at least moderate severity, days of headache with any severity, total hours of headache with at least moderate severity, total hours of headache with any severity, days of use of migraine-specific acute medications, days with nausea or vomiting, days with photophobia and phonophobia etc.) **during the 4-week period** after each dose of study drug will be calculated using formula (2).

The change from baseline in the number of migraine days **during the 4-week period** after the 1st dose of study drug will be derived using only the 1st month diary data. Since the patients randomized to both active treatment arms receive the same dose of TEV-48125 675-mg at their 1st dosing, their data will be combined for the analysis.

The change from baseline in weekly number of headache days of at least moderate severity or migraine days for week 1 (Day 1-7), week 2 (Day 8-14), week 3 (Day 15-21) and week 4 (Day 22-28) after the 1st dose of study drug will be derived using the 1st 28-day diary data. The baseline values and the postbaseline values will be derived using formula (5) and (6) in Section 6.2.1 respectively, and **the change** is calculated as **postbaseline value – baseline value**.

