2. STUDY DESIGN

2.1. General Design and Study Schema

This is a 16-week, multicenter, randomized, double-blind, placebo-controlled, parallel-group study to compare the safety, tolerability, and efficacy of 2 dose regimens of sc TEV-48125 and placebo in adults with CM. The study consists of a screening visit, a 28-day run-in period, and a 12-week (84-day) treatment period, including a final evaluation at week 12 (end-of-treatment [EOT] visit, approximately 4 weeks [28 days] after the final dose of study drug).

This study will include female and male patients, aged 18 to 70 years, inclusive, with a history of migraine for at least 12 months and CM (as defined by International Classification of Headache Disorders, 3rd edition [ICHD-3] criteria [[Classification Committee of the IHS, 2013](#)]). The diagnosis will be prospectively confirmed via a review of headache data recorded daily during a 28-day run-in period in an electronic headache diary device.

Patients using no more than 1 preventive medication at the time of study enrollment will be allowed to remain on the medication if the medication has at least moderate evidence of efficacy for migraine ([Silberstein et al 2012](#)). Patients should not initiate any preventive migraine medications (presented in protocol Appendix B) at the time of the screening visit, and will not be allowed to initiate these medications after study start. A small subgroup of patients (approximately 30%) will be allowed to use concomitant migraine preventive medications (presented in protocol Appendix A), and no changes in these medications will be allowed until the last study assessments are complete. Patients will be allowed to use acute medications to treat acute migraine attacks, as needed.

After completing the informed consent process (screening visit [visit 1]), patients will be screened for eligibility. Eligible patients will enter a 28-day run-in period. Headache information will be captured daily throughout study participation using the electronic headache diary device. After completing the run-in period, patients will be asked to return to the study center on day 0 (visit 2). Patients who have confirmed CM and meet all other eligibility criteria (including electronic headache diary compliance criteria during the 28-day run-in period) will be randomly assigned in a 1:1:1 ratio to 1 of 3 treatment groups:

- sc administration of 675 mg of TEV-48125 at visit 2 followed by monthly sc TEV-48125 at 225 mg

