3.3. Full Analysis Set

The full analysis set (FAS) will include all patients in the ITT population who receive at least 1 dose of study drug and have at least 10 days of post baseline efficacy assessments on the primary endpoint. The FAS will be used for all efficacy analysis.

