4.5. Handling Withdrawals and Missing Data

If a patient has ≥ 10 days of e-diary data after 1st dose of the study drug, his/her monthly average number of days/hours of efficacy variables *during the 12-week period* or monthly number of days/hours of efficacy variables *during the 4-week period* will be prorated to 28 days.

Multiple imputation (MI) method will be applied on the primary variable as sensitivity analyses. The methods will be described in detail in Section 6.2.3.

A patient's monthly number of days/hours of efficacy variables *during the 4-week period* after each dose of study drug will be calculated for months 1, 2, and 3. If a patient has missing diary

days when calculating the monthly variables, the following method will be used to handle the missing data.

- If a patient has ≥ 10 days of e-diary data for a month, the monthly number of days/hours of efficacy variables will be prorated to 28 days for that month.
- If a patient has < 10 days of e-diary data for a month, the monthly number of days/hours of efficacy variables will be considered as missing.

The weekly number of headache days of at least moderate severity and migraine days will be calculated for the patients' first 28 calendar days of diary data after the 1st dose of study drug. Each week is defined as 7 calendar days counted from the 1st dose date. If a patient has missing diary days when calculating the weekly variables, the following method will be used to handle the missing data.

- If the patient has ≥ 3 days of e-diary data for a week, the weekly number of days of efficacy variables will be prorated to 7 days for that week.
- If the patient has < 3 days of e-diary data for a week, the weekly number of days of efficacy variables will be considered as missing for that week.

The missing questionnaire items handling for the MSQOL questionnaire ([Appendix D](#)) is discussed in [Appendix E](#): scoring instruction for MSQOL.

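### A study completer can be counted as a total (100%) responder over 12 weeks on as few as 10 of 84 diary days, which can only inflate the exploratory 100% response rates

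*SAP*

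**What the plan says.** Section 2.2.3 lists total (100%) reduction over 12 weeks as an exploratory endpoint, for headache days of at least moderate severity and for migraine days. Section 6.4.1.1 defines it: "The patient is considered as a responder reaching 50%, 75% or 100% reduction if his/her percent reduction is 50% or more", and correspondingly for 75% and 100%. A patient who leaves the study early is a non-responder. No condition on diary completeness is added.

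The percent reduction is formula (4) in Section 6.1, with formula (1) as the post-baseline value. Formula (1) divides event days by days recorded in the diary and multiplies by 28. Section 4.5 permits this proration on the following condition: "If a patient has ≥ 10 days of e-diary data after 1st dose of the study drug". Membership of the full analysis set needs no more; patients must "have at least 10 days of post baseline efficacy assessments on the primary endpoint" (Section 3.3).

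For a single month the SAP is stricter. With fewer than 10 "days of e-diary data for a month, the monthly number of days/hours of efficacy variables will be considered as missing" (Section 4.5).

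**The concern.** Prorating a count is reasonable for a mean if unrecorded days resemble recorded ones. It is not neutral for the condition that no event occurred. Unrecorded days drop out of both parts of formula (1), so zero events on any subset of days gives a 12-week value of zero. A patient with truly no event days scores zero on every subset, while a patient with some event days may also score zero by chance. The error runs one way, and it grows as the diary gets thinner.

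The SAP treats a patient who drops out as a non-responder, but a patient who stays in the study and stops recording as fully observed. Total response may be uncommon in chronic migraine; if so, a few such patients could move the rate and the Cochran-Mantel-Haenszel comparison in Section 6.4.2.1.

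**Working it through.** **Inputs from the SAP.** Treatment period: "12-week (84-day) treatment period" (Section 2.1). Minimum for the 12-week value: 10 recorded days in total (Section 4.5). Minimum for a monthly value: 10 recorded days in that month (Section 4.5). The SAP gives no figure for sparse diaries or for the expected 100% rate, so there is no stated figure to reproduce on this point.

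**Step 1: the rule applied.** A completer with 10 recorded days and 0 event days has formula (1) = 0/10 × 28 = 0. Formula (4) = (baseline − 0)/baseline × 100% = 100%. The patient is a total responder on 10/84 = 11.9% of days.

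**Step 2: is this blocked elsewhere?** No. Diary compliance is mentioned only for the run-in (Section 2.1). The per-protocol set has no diary condition (Section 3.4). Multiple imputation covers only the primary variable (Sections 4.5 and 6.2.3.2).

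**Step 3: chance of a false total response.** Assume independent days and a true rate of r event days per 28. Then P(no event in n recorded days) = (1 − r/28)^n.

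| True r per 28 | n = 10 | n = 30 | n = 84 |
|---|---|---|---|
| 2 | 0.477 | 0.108 | 0.002 |
| 4 | 0.214 | 0.010 | about 0 |
| 6.5 (assumed baseline 13, halved) | 0.071 | 0.0004 | about 0 |

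For example, (26/28)^10 = 0.477.

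**Step 4: the 75% level, same method.** The limit is the largest whole number of event days not above 0.25 × baseline × n/28.

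| Assumed baseline | True reduction | Called on 10 days | Called on 84 days |
|---|---|---|---|
| 13 | 60% (true non-responder) | 0.42 | 0.04 |
| 8 | 80% (true responder) | 0.56 | 0.80 |
| 20 | 80% (true responder) | 0.57 | 0.86 |

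Sparse diaries create false responders and lose true ones.

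**Step 5: the monthly limit applied to the 12-week status.**

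| Recorded days, months 1/2/3 | Total | 12-week value allowed now | All months evaluable |
|---|---|---|---|
| 10/0/0 | 10 | yes | no |
| 4/3/3 | 10 | yes | no |
| 9/9/9 | 27 | yes | no |
| 28/28/9 | 65 | yes | no |
| 10/10/10 | 30 | yes | yes |

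Requiring 10 days in each month raises the minimum from 10 to 30 of 84 days (35.7%). At r = 2, the chance of a false total response at the minimum falls from 0.477 to 0.108.

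**Step 6: illustration of size, on assumption only.** Suppose 1% to 3% of the 289 completers per arm planned in Section 2.3 had exactly 10 recorded days. That is 2.9 to 8.7 patients. At 0.071 each, 0.2 to 0.6 are falsely counted; at 0.477 each, 1.4 to 4.1.

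**The case against.** **The endpoint is a prorated rate, and regulators asked for the 10-day rules.** Section 2.2.3 speaks of a reduction in a monthly average, and the amendment history attributes the 10-day limits to FDA review comments. Both are true. But a 100% reduction in a rate means a rate of zero, and that is the value for which a short record is least informative. The amendment history does not suggest that the total-response endpoint was considered when the limits were set.

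**The effect may be very small.** This stands. The number of sparse diaries is unknown. The diary is reviewed at each visit (Table 1), and any post-baseline compliance requirement may sit in the protocol, which was not available. The 48% figure needs a patient already down to 2 event days per 28. The rule is the same in all arms, and nothing shows that it favors one of them.

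**A reader might infer that the 75% rate is overstated too.** Step 4 does not support that; misclassification at 75% runs in both directions.

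**A reader might infer that the SAP contradicts itself**, because a patient could be a 12-week total responder and yet not a sustained 50% or 75% responder. Sustained response is a different endpoint by design: it requires the threshold in month 1 and then also in months 2 and 3 ("In addition if the patient also has 50% reduction or more in month 2 and 3"). Section 6.4.1.1 does not say in words how a missing month is scored there. What differs is the amount of diary data required, and that is not a contradiction.

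**Conclusion.** The point holds for the exploratory total-response endpoints, for headache days of at least moderate severity and for migraine days, and is minor. Ten recorded days are enough for a 12-week total response in a completer, and the resulting error can only raise the 100% rate. That direction needs only that the recorded entries are accurate. The sizes in Step 3 also assume independent days; clustering of event days would change them. The net effect on the trial's 100% rates cannot be given from the SAP, and Step 6 is an illustration.

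No confirmatory claim is affected, because these endpoints are outside the fixed sequence in Section 4.4. The secondary 50% responder and the continuous variables share the 10-day rule, but the one-way argument is specific to a count of zero and does not carry over to them.

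**What to change.** Add one sentence to Section 6.4.1.1: for total (100%) reduction over 12 weeks, in either variable, a patient is a responder only if months 1, 2 and 3 each have at least 10 diary days; otherwise the patient is a non-responder, as for early discontinuation. Report the count under the current rule alongside. Leave the 75%, secondary 50% and continuous endpoints unchanged. The change belongs before database lock and unblinding (Section 2.5.2).

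Cost: the 100% rate becomes slightly lower, and a few true total responders with one sparse month are lost. A 28/28/9 diary with no events in 65 days would fail, although at 2 event days per 28 such a record has only a (26/28)^65 = 0.8% chance. The 100% endpoints would also follow a different diary rule from the other responder endpoints. The limit reduces the inflation but does not remove it: 11% remains at 30 days for that same patient. Showing both counts lets a reader see how much depends on the rule.

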6.4.1.2. Migraine-Specific Quality of Life

The 14-item MSQOL (see [Appendix D](#)) questionnaire is designed to measure how migraines affect and/or limit daily functioning across 3 domains: Role Function-Restrictive domain comprising 7 items assessing how migraines limit one's daily social and work-related activities; Role Function-Preventive domain comprising 4 items assessing how migraines prevent these activities, and Emotional Function domain comprising 3 items assessing the emotions associated with migraines. Raw dimension scores are computed as a sum of item responses and rescaled to a 0 to 100 scale such that higher scores indicate better quality of life. [Appendix E](#) provides the scoring instructions on how to rescale the raw score to the scales that will be used for the analysis.

6.4.1.3. EuroQol-5 Dimension Questionnaire

The EQ-5D-5L questionnaire ([Appendix F](#)) is a standardized questionnaire that assesses overall state of health. The EQ-5D-5L consist of 2 parts. In part 1, patients rate their health state in 5 domains: mobility, self-care, usual activities, pain/discomfort, and mood, using a scale of 1 to 5 where 1 = no problems, 2 = slight problems, 3 = moderate problems, 4 = severe problems, and 5 = extreme problems. In part 2, patients rate their health state on a 100 mm visual analog scale; a rating of 0 represents the worst imaginable health state, and a rating of 100 represents the best imaginable health state.

6.4.1.4. Patient Health Questionnaire

The PHQ (Appendix G) is a 9-item questionnaire with each item corresponding to 1 criterion of the Diagnostic and Statistical Manual for Mental Disorders 4th edition diagnostic criteria for major depressive disorder. Each of the items is scored on a scale of 0 (“not at all”), 1 (“several days”), 2 (“more than half the days”), and 3 (“nearly every day”) based on the frequency of symptoms during the past 2 weeks (Spitzer et al 1999). The PHQ-2 was developed from the PHQ-9 to rapidly screen for depression and consisted of the first 2 questions of the PHQ-9. The PHQ-2 and the PHQ-9 are validated measures for detecting and monitoring depression, anxiety, and somatization (Kroenke et al 2010).

Patients will complete the PHQ-2 at baseline (visit 2) and the EOT visit (visit 5). If the PHQ-2 is positive (ie, a score of ≥ 3), patients will complete questions 3 through 9 (unique questions) of the PHQ-9.

6.4.1.5. Work Productivity and Activity Impairment Questionnaire: General Health V2.0

The generic version of the WPAI: General Health (GH) (Appendix H) questionnaire measures the overall effect of health on productivity at work and daily activities. The specific health problems version of the WPAI questionnaire allows investigators to attribute productivity and activity impairment issues to specific health conditions.

The following scores will be derived based on the WPAI:GH questionnaire. Multiply scores by 100 to express in percentages.

- percent work item missed due to health: $\frac{Q2}{Q2+Q4}$
- percent impairment while working due to health: $\frac{Q5}{10}$
- percent overall work impairment due to health: $\frac{Q2}{Q2+Q4} + \left[\left(1 - \frac{Q2}{Q2+Q4} \right) \times \frac{Q5}{10} \right]$
- percent activity impairment due to health: $\frac{Q6}{10}$

6.4.1.6. Patient’s Global Impression of Change

The PGIC scale (Appendix I) is a validated generic tool for assessment of overall change in the severity of illness following treatment. Patients will rate how they feel now compared with how they felt before receiving study drug on a 7-point scale where 0 is “No change,” and 7 is “A great deal better”.

Based on the PGIC assessment, a dichotomous scale of “Yes” or “No” will be derived. A favorable change is score of 5-7 = ‘Yes’, which means there is significant improvement with the treatment. If the response is 1-4 = ‘No’, it is considered no significant change.

6.4.2. Exploratory Efficacy Analysis

6.4.2.1. Electronic Headache Diary Data

Cochran Mantel-Haenszel test stratified by baseline preventive migraine medication use (yes/no) will be implemented for analyzing the responder type of exploratory efficacy endpoints. The SAS Proc FREQ will be used to carry out this analysis.

An ANCOVA method defined in Section 6.2.2 and an MMRM model defined Section 6.2.3.1 will be implemented for the following exploratory endpoints analysis.

- mean change from baseline (28-day run-in period) in the monthly average number of headache days of any severity during the 12-week period after the 1st dose of study drug
- mean change from baseline (28-day run-in period) in the monthly average number of headache hours of any severity during the 12-week period after the 1st dose of study drug
- mean change from baseline (28-day run-in period) in the monthly average number of headache hours of at least moderate severity during the 12-week period after the 1st dose of study drug
- mean change from baseline (28-day run-in period) in the monthly average number of days with nausea or vomiting during the 12-week period after the 1st dose of the study drug
- mean change from baseline (28-day run-in period) in the monthly average number of days with photophobia and phonophobia during the 12-week period after the 1st dose of study drug

The 2 active treatment groups data will be combined to compare with the placebo group by ANCOVA method for analyzing the mean change from baseline in the number of migraine days during the 4-week period after the 1st dose of study drug.

Similar to the sensitivity analysis for the primary efficacy variable described in Section 6.2.3.1, an MMRM model will be implemented to estimate the mean change from baseline for the following endpoints by week after the 1st dose of study drug.

- mean change from baseline in the weekly number of headache days of at least moderate severity
- mean change from baseline in the weekly number of migraine days

LS means for the treatment groups, LS means and corresponding 95% confidence intervals for the treatment differences (TEV-48125 - placebo), and associated p-values will be calculated by week.

The LS means \pm SE of e-diary efficacy variables estimated by MMRM will be plotted by week for each treatment group.

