2.3. Sample Size and Power Considerations

In a Phase 2b study in CM patients, a treatment difference of 1.7 days of monthly average headache days of at least moderate severity between the TEV-48125 675/225/225 mg and placebo treatment groups was observed. A sample size of 867 patients (i.e., 289 evaluable patients completing the study per treatment group) results in at least 90% power for the study to succeed (assuming a common standard deviation [SD] of 6.29 days) at an alpha level of 0.05. Assuming a 15% discontinuation rate, 340 patients per treatment group will be randomized.

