9. mean change from baseline (28-day run-in period) in the monthly average number of migraine days during the 12-week period after the 1st dose of study drug for the TEV 48125 675 mg/placebo/placebo treatment group versus the placebo treatment group
10. mean change from baseline (28-day run-in period) in the monthly average number of headache days of at least moderate severity during the 12-week period after the 1st dose of study drug for the TEV 48125 675/225/225 mg treatment group versus the placebo treatment group in patients not receiving concomitant migraine preventive medications
11. mean change from baseline (28-day run-in period) in the monthly average number of headache days of at least moderate severity during the 12-week period after the 1st dose of study drug for the TEV 48125 675 mg/placebo/placebo treatment group versus the placebo treatment group in patients not receiving concomitant migraine preventive medications
12. mean change from baseline (day 0) in disability score, as measured by the HIT-6 at 4 weeks after administration of the last (3rd) dose of study drug for the TEV 48125 675/225/225 mg treatment group versus the placebo treatment group
13. mean change from baseline (day 0) in disability score, as measured by the HIT-6 at 4 weeks after administration of the last (3rd) dose of study drug for the TEV 48125 675 mg/placebo/placebo treatment group versus the placebo treatment group

If the resulting 2-sided p-value from the first comparison is ≤ 0.05 , then the next comparison of interest will be interpreted inferentially at the alpha level of 0.05. This process will continue either until all comparisons of interest are interpreted inferentially or until the point at which the resulting 2-sided p value for a comparison of interest is >0.05 . At the point where $p > 0.05$, no further comparisons will be interpreted inferentially.

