4.6. Study Days and Visit Windows

Study days will be numbered relative to the 1st day of study drug administration. The start of treatment (visit 2 or day 1) is defined as the date on which a patient takes the 1st dose of study drug, as recorded on the study drug administration CRF. Days will be numbered relative to study drug start (i.e., ..., -2, -1, 1, 2, ...; with day 1 being the start of study drug and day -1 being the day before the start of study drug).

The 4-week (28-day) visit windows for the e-diary based efficacy endpoints will be determined based on the actual dosing day. The run-in phase is defined as day -28 to -1 before the 1st injection on day 1. Treatment phase including month 1, 2 and 3 is from the beginning of the 1st injection of study drug to visit 5/day 84 or the end of treatment visit. The 3-month visit windows are separated by each dosing date/time. Month 1 is from the date/time of the 1st dose of study drug administration on day 1 to the date/time just before the 2nd dose. Month 2 is from the date/time of the 2nd dose to the date/time just before the 3rd dose. Month 3 is from the date/time of the 3rd dose to the end of the study on day 84 approximately.

Throughout this document, all by month efficacy summaries for the headache data will refer to these visit windows.

The weekly (7-day) windows for calculating the weekly efficacy endpoints for the first 28 days will be determined based on the 1st dosing day. The first week is from day 1 to day 7, the second week is from day 8 to day 14, the third week is from day 15 to day 21, and the fourth week is from day 22 to day 28. Only the days between the first and the second dose will be included.

For all other by-visit summaries, if there are multiple assessments at a postbaseline visit then the last non-missing assessment at that visit will be used for the summary. This includes assessments at the scheduled and unscheduled visits.

Endpoint for analyses and summaries is the last observed postbaseline data. For patients who withdraw from the study, their safety data at the early termination visit will be excluded from the by-visit summaries but will be included in the endpoint summaries.

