6.3.1. Variable Definition

6.3.1.1. Electronic Headache Diary Data

The change from baseline in the monthly average number of days of secondary efficacy variables (e.g., migraine days, days with at least moderate severity, days of use of any acute headache medications etc.) *during the 12-week period* after the 1st dose of study drug will be derived similar to the primary variables using the e-diary data collected through the corresponding headache diary questions ([Appendix A](#)). The baseline values and the postbaseline values will be calculated using formula (3) and (1) respectively. *The change* is calculated as *postbaseline value – baseline value*.

The percent reduction in the monthly average number of headache days of at least moderate severity *during the 12-week period* after the 1st dose of study drug will be calculated by formula (4) in Section 6.1. The patient is considered as a responder if the percent reduction is 50% or more. If a patient is early discontinued from the study, he/she will be counted as a non-responder.

The change from baseline (run-in period) in the number of headache days of at least moderate severity *during the 4-week period* after the 1st dose of study drug will be derived similar to the primary endpoint using only the 1st month diary data. Since the patients randomized to both active treatment arms receive the same dose of TEV-48125 675-mg at their 1st dosing, their data will be combined for analyzing the endpoints *during the 4-week period* after the 1st dose of study drug.

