6.4.2.6. Patient's Global Impression of Change Scale

The percentage of patients' dichotomous scale of " Yes" or "No" rated by PGIC assessments at 4-week after each dose will be analyzed by Cochran Mantel-Haenszel test stratified by baseline preventive migraine medication use (yes/no) as described in Section 6.3.2.

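### The weekly diary endpoints all fall before dose 2, yet they are analysed by treatment group with no pooling statement, against the SAP's rule for the first 4 weeks

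*SAP*

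**What the plan says.** **The rule.** SAP Section 6.3.1.1 explains that patients in both active arms "receive the same dose of TEV-48125 675-mg at their 1st dosing, their data will be combined for analyzing the endpoints" of the 4-week period after dose 1. Section 7.2 confirms the premise: both arms receive three active injections at visit 2 and differ only from visit 3.

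**Where it is applied.** Section 6.3.2 combines the arms for the month-1 change in headache days of at least moderate severity. Sections 6.4.1.1 and 6.4.2.1 combine them for the month-1 change in migraine days.

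**Where it is not.** Section 2.2.3 places the weekly headache-day and migraine-day endpoints in the same 4-week period. Section 4.6 says of the weekly windows: "Only the days between the first and the second dose will be included". Section 6.4.2.1 sends these endpoints to an MMRM like that of Section 6.2.3.1, asks for LS means for the treatment groups and weekly p-values, and has the LS means "estimated by MMRM will be plotted by week for each treatment group". The default in Section 6.1 is presentation by randomized group unless otherwise noted, and nothing is noted here.

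**PGIC.** Section 6.4.2.6 covers the percentages "rated by PGIC assessments at 4-week after each dose will be analyzed by Cochran Mantel-Haenszel test" and states no arm structure.

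**The concern.** The weekly endpoints are there to show how soon an effect appears. Every day that enters them comes before the two active arms diverge, so for this purpose the arms are one treatment. Section 6.4.2.1 therefore pools migraine days for month 1 but not for the four weeks that make up that month.

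Two things are at stake. Precision is lost, because each contrast uses half of the available active patients. The output may also contradict itself: two onset curves and two sets of weekly p-values for one treatment, where one arm may reach p ≤ 0.05 in a given week and the other not, by chance alone. Two programmers working from Sections 6.3.1.1 and 6.4.2.1 could also build different tables.

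**Working it through.** **Inputs (SAP Sections 2.1, 2.3 and 4.4).** The planning effect is "a treatment difference of 1.7 days of monthly average headache days of at least moderate severity". The common SD is 6.29 days, with 289 evaluable patients per arm, 340 randomized per arm after 15% discontinuation, and 1:1:1 allocation. Tests are two-sided "at an alpha level of 0.05".

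**1. Reproduce the plan's own figure.**
- n per arm = 2 × (1.960 + 1.282)² × 6.29² / 1.7² = 288, against 289 stated.
- Power with 289 per arm is 90.1%, which agrees with a sample size that "results in at least 90% power for the study to succeed".
- 289 / 0.85 = 340. The design reproduces.

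**2. Standard error, per arm against pooled.**
- Per arm: SD × √(1/n + 1/n) = SD × √(2/n).
- Pooled: SD × √(1/n + 1/(2n)) = SD × √(1.5/n).
- Ratio pooled / per arm = √(1.5/2) = 0.866, a 13.4% reduction. Inverse: 1/0.866 = 1.155, so per-arm analysis carries a 15.5% larger SE.

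The ratio depends only on equal arm sizes and a common variance, so it applies to the weekly counts whatever their scale.

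**3. What that means in days and power.** The SAP gives no weekly effect or SD. Its monthly inputs are used here as an assumed stand-in, with a range of smaller effects.
- Per-arm SE = 6.29 × √(2/289) = 0.523 days; 95% CI half-width 1.03 days.
- Pooled SE = 6.29 × √(1/289 + 1/578) = 0.453 days; half-width 0.89 days.

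| True difference (days) | Power per arm | Power pooled |
|---|---|---|
| 0.85 | 36.9% | 46.6% |
| 1.275 | 68.3% | 80.3% |
| 1.7 | 90.1% | 96.3% |

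**4. How often two identically treated arms disagree.** This was simulated with two active arms sharing one placebo arm, 289 per arm, 400,000 draws.

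| True difference (days) | Exactly one arm significant |
|---|---|
| 0 | 8.1% |
| 0.85 | 31.5% |
| 1.275 | 29.4% |
| 1.7 | 13.4% |

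With no effect, the chance of at least one nominally significant result per week and endpoint is 9.0% for two arm-wise tests and 5.0% for one pooled test. By-arm testing gives 4 weeks × 2 endpoints × 2 arms = 16 weekly p-values; pooling gives 8.

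**The case against.** **The weekly wording may be loose rather than an instruction for two tests.** Section 6.4.2.1 writes the contrast as TEV-48125 minus placebo without naming a regimen, and the rule in 6.3.1.1 could be read as already covering these endpoints. This stands in part: the SAP does not expressly order two separate weekly tests. However, Sections 6.2.2 and 6.2.3.1 use the same contrast label. Section 6.2.2 plainly compares each regimen with placebo, and the model in 6.2.3.1 has no pooled treatment term. The general rule sits under the secondary variables, and the exploratory text in 6.4.1.1 repeats it only for month-1 migraine days. The conflict is therefore real, though it is a matter of wording.

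**A reader might infer that every measure taken before dose 2 breaks the rule.** The documents do not support that.
- Month-1 response is not a stand-alone endpoint. Sections 2.2.3 and 6.4.1.1 require the response to be sustained through months 2 and 3, when the arms differ, so analysis by arm is right.
- For the PGIC at visit 3, the SAP is silent; per-arm analysis follows only from the default in Section 6.1. It is also a point-in-time rating, which the 4-week rule reaches only by extension. The rationale still applies, because Table 1 places assessments before dosing.
- MSQOL and the monthly MMRMs include time points after dose 2 in the same model and need separate arms.

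**The consequence is small.** This stands. Each arm-wise comparison with placebo remains unbiased, the SAP attaches no formal claim to the weekly results, and the month-1 headache-day comparison in the fixed sequence of Section 4.4 is already pooled.

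**Conclusion.** The point holds for the weekly headache-day and migraine-day endpoints. They meet the condition under which Section 6.3.1.1 combines the active arms, but Section 6.4.2.1 presents them by treatment group. The firm size is the 15.5% larger standard error, which rests only on equal evaluable numbers and a common variance. The power and disagreement figures are illustrative, because they borrow the monthly effect and SD.

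For the PGIC at visit 3 this is a request for clarification, not a breach. Nor should the point be read as a threat to error control: the rule that begins "If the resulting 2-sided p-value from the first comparison is ≤ 0.05" governs 13 listed comparisons, and none of these exploratory measures is among them. Severity is low, but the change costs almost nothing.

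**What to change.** - **Section 6.4.2.1:** state that the weekly MMRM for headache days of at least moderate severity and for migraine days compares the combined active arms with placebo, using a two-level treatment factor, and that by-arm weekly results and plots are descriptive only. A two-level factor suits this model throughout, since all of its time points precede dose 2.
- **Section 6.4.2.6:** as a clarification, state that the PGIC at visit 3 is compared as combined active arms against placebo, and the later PGIC assessments by arm.
- **Leave by arm:** sustained response, MSQOL and the monthly MMRMs.

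The cost is two sentences and one derived treatment variable. No new data are needed. Keeping the by-arm descriptives adds one set of tables. The change should be made before unblinding.
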